3.3.6. Presentations by Study Visit

Nominal study visits as obtained from the CRF or laboratory will be utilized for summary displays of efficacy endpoints. Unscheduled and early termination (ET) visits will be windowed based on study day, according to the table below. All assessments will be presented in the listings. If assessments are collected multiple times within a given study visit, the result closest to the scheduled visit date will be used for summary presentations. If two measurements have the same distance to the expected date, the earlier value will be used. If a scheduled assessment and an unscheduled or ET assessment are collected within a given visit, the value from the scheduled assessment will be chosen over the value from the unscheduled assessment.

Study Day	Windowed Study Visit	Additional Details
2 – 20	Week 2	
21 – 34	Week 4	
35 – (date of randomization to Period 2)	Week 6	If subject is not randomized to Period 2, use study day 42 as upper limit
(date of randomization to Period 2) + 1 – 62	Week 8	

63 - 76	Week 10	
77 – (date of randomization to Period 3)	Week 12	If subject is not randomized to Period 3, use study day 84 as upper limit
(date of randomization to Period 3) + 1 – 104	Week 14	
105 – 118	Week 16	
119 – Exit	Week 18	

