1.1. STUDY OVERVIEW

Protocol HTD1801.PCT003 is a Phase 2, randomized, double-blind study which consists of a placebo- and dose-controlled parallel group period, a dose-controlled extension period, and a placebo-controlled randomized withdrawal period with the intent of comparing multiple doses of investigational product (HTD1801) to placebo. Approximately 60 patients with Primary Sclerosing Cholangitis (PSC) will be enrolled as subjects. Upon confirmation of eligibility, subjects will be randomized in Period 1 in a 1:1:1 ratio, stratified by inflammatory bowel disease (IBD) diagnosis and ursodiol (UDCA) status, to one of the following treatment arms:

- **Treatment Arm 1:** HTD1801 500 mg twice daily (BID)
- **Treatment Arm 2:** HTD1801 1000 mg BID
- **Treatment Arm 3:** Placebo BID.

Subjects will receive the treatment to which they are randomly assigned for 6 weeks during the first period.

In response to the COVID-19 pandemic, enrollment into the study was prematurely stopped on 25th March 2020. This impacted 3 subjects who had been randomized but had not yet initiated dosing. There may be additional restrictions associated with COVID-19 that may impact sites' ability to schedule subjects for in-clinic visits and thus, complete all protocol-required assessments. These will be noted as protocol deviations related to COVID-19 should they occur. These measures were put into place following the issuance of the FDA Guidance on Conduct of Clinical Trials of Medical Products during COVID-19 Pandemic (March 2020 and April 2020).

See [Section 3.2](#) for additional details on Period 1 randomization.

Following the completion of the first period, subjects are eligible to enroll in Period 2 which is a 6-week extension period. During this period, subjects who were previously randomized to 500 mg or 1000 mg BID in Period 1 will continue to receive the same dose. Subjects who were previously randomized to placebo will be randomized in a 1:1 ratio to receive 6 weeks of either 500 mg or 1000 mg BID. This period will continue to be double-blind.

Following the completion of Period 2, the 6-week treatment extension period, all subjects will be randomized in a 1:1 ratio to either continue on the active treatment they received in the second period or be assigned to placebo.

An independent Data and Safety Monitoring Board (DSMB) will provide additional safety oversight.

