3.3.7. Definitions and Terminology

Age

The age of a subject is defined as the number of whole years between the subject's birth date and the Period 1 treatment start date.

Day 1 (Baseline)

Day 1 is the earliest day that study drug is initiated in Period 1.

Study Day

Study Day is defined relative to Baseline (Day 1). Thus, the study day of an event is calculated as:

Study Day = event date – date of Day 1 (+ 1 if event date \geq date of Day 1).

Study Visit

Study Visit is the nominal visit as recorded on the CRF.

Weeks of Exposure

Weeks of exposure is calculated as the $(\text{Last Day on Study Drug} - \text{First Day on Study Drug} + 1) / 7$ within each period.

Treatment Compliance

Treatment compliance is calculated as the Number of Days of Dosing / Expected number of days of dosing within each period.

Baseline Value

For purposes of analysis, the baseline value is defined as the last non-missing value obtained prior to initiation of study drug.

Change from Baseline

Change from baseline for a given endpoint is defined as the Study Day X value minus the Baseline Value.

Adverse Event (AE)

An AE is defined as any untoward medical occurrence associated with the use of a drug in humans, whether or not considered drug related. An AE can be any unfavorable and unintended sign (including an abnormal laboratory finding), symptom, or disease (new or exacerbated) temporally associated with the use of the investigational product, regardless of whether it is considered to be related to the investigational product. All adverse events will be recorded on the Adverse Event CRF.

Treatment-emergent Adverse Event (TEAE)

A TEAE will be an AE that occurred during the study after the first dose of study drug or that was present prior to dosing and exacerbates after the first dose of study drug. Additionally, it is assumed that an Adverse Event which was reported to have started on Day 1 without an associated onset time occurred after the initiation of study drug.

Concomitant Medications

Concomitant medications are those medications taken on or after the initiation of study drug. This definition includes medications started prior to the initiation of study drug but continuing concomitantly with study drug.

Prior Medications

Prior medications are those medications taken prior to the initiation of study drug.

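### Early-termination and unscheduled values in Periods 2 and 3 are windowed on days since Period 1 Day 1, so a late re-randomization shifts their visit labels within the period

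*SAP*

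**What the plan says.** SAP 3.3.6 keeps the nominal label for scheduled visits. For the rest: "Unscheduled and early termination (ET) visits will be windowed based on study day, according to the table below". A scheduled value takes precedence over an unscheduled or early-termination (ET) value at the same visit.

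SAP 3.3.7 fixes the origin of the count: "Study Day is defined relative to Baseline (Day 1"), and "Day 1 is the earliest day that study drug is initiated in Period 1". Nothing resets it at Period 2 or Period 3.

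The table mixes two anchors. Re-randomization dates set the outer edges of a period, while the inner edges are fixed Study Days:

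- Week 8 is "date of randomization to Period 2) + 1 – 62", and Week 10 is Days 63 to 76.
- Week 12 is "77 – (date of randomization to Period 3"), with the note "If subject is not randomized to Period 3, use study day 84 as upper limit".
- Week 14 is "date of randomization to Period 3) + 1 – 104", Week 16 is Days 105 to 118, and Week 18 runs from Day 119 to exit.

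On scheduling, SAP 1.1 says COVID-19 restrictions may affect sites' "ability to schedule subjects for in-clinic visits and thus, complete all protocol-required assessments". SAP 3.2 gives a 45-day drug supply for each 42-day period, which is 3 days of slack. Neither document states a permitted window around scheduled visits.

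**The concern.** Periods 2 and 3 begin on the subject's own re-randomization date, but the cut points inside them assume that this date was on schedule. If it was late, a value from early in the period can be labelled as the end of the period.

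SAP 5.2.4 lists ALP change from Week 6 to 12 and from Week 12 to 18, and responder proportions at the end of each period. SAP 3.3.4 allows no imputation of values. Under a delay, the window table can nevertheless fill the Week 12 or Week 18 cell with a short-exposure value from an early leaver, which amounts to an unstated carry-forward. It can also refuse the Week 12 label to a value at full period length. With about 60 subjects split over several Period 2 and Period 3 groups, a few such records could change a tabulated proportion.

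**Working it through.** **Inputs.** Cut points and the Day 84 cap: SAP 3.3.6. Origin of Study Day: SAP 3.3.7. Period length of 42 days and supply slack of 3 days: SAP 1.1 and 3.2. Delay is measured against Study Days 42 and 84. Its size is not in the documents, so 0 to 21 days is an assumed range.

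**Reproducing the table.** With nominal visits at 7 × week, the cut points are midpoints between neighbouring visits: (14+28)/2 = 21, (28+42)/2 = 35, (56+70)/2 = 63, (70+84)/2 = 77, (98+112)/2 = 105, (112+126)/2 = 119. All six match, so the table is built for on-time subjects.

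**Days in period when the end-of-period window opens.** Let R2 and R3 be the Study Days of re-randomization to Periods 2 and 3. Elapsed days are 77 − R2 for Week 12 and 119 − R3 for Week 18. Without entry to Period 3, Week 12 closes at 84 − R2.

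| Delay (days) | R2 | Week 12 opens | Week 12 closes, no Period 3 | R3 | Week 18 opens |
|---|---|---|---|---|---|
| 0 | 42 | 35 | 42 | 84 | 35 |
| 3 | 45 | 32 | 39 | 87 | 32 |
| 6 | 48 | 29 | 36 | 90 | 29 |
| 7 | 49 | 28 | 35 | 91 | 28 |
| 14 | 56 | 21 | 28 | 98 | 21 |
| 21 | 63 | 14 | 21 | 105 | 14 |

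Delay at Period 3 is cumulative over both earlier periods. Using the full supply slack gives R2 = 45 and R3 = 42 + 3 + 42 + 3 = 90, so the labels open at 32 and 29 days instead of 35.

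**Gaps and overlaps.**

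- Week 8 runs from R2 + 1 to 62, so it is empty if R2 is 62 or later.
- Week 6 runs to R2 and Week 10 starts at 63. If R2 is 63 or later, Days 63 to R2 lie in both rows (for R2 up to 76).
- Likewise, Week 14 is empty if R3 is 104 or later.
- For a subject not randomized to Period 3, a value 42 days into Period 2 falls on Study Day R2 + 42. This exceeds 84 after any delay, so it cannot be Week 12. With R2 = 64 it falls on Day 106, which read literally is the Week 16 row, in a period the subject never entered. For that subject only values 77 − 64 = 13 to 84 − 64 = 20 days into the period can be called Week 12.

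**The case against.** The case against giving this much weight is strong, and most of it stands.

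- **Delay is not documented.** A label two to three weeks into a period needs re-randomization 14 to 21 days late. Within the planned slack the shift is 3 to 6 days, which is immaterial. A reader might infer that the SAP expects long COVID-19 delays, but it says only that restrictions may have an effect. SAP 3.2 has 42 subjects randomized before the manual process began in November 2019 and 17 afterwards. Even if the last of the 42 started on 30 November, on schedule they reached Week 12 by 22 February 2020 (84 days later), before enrollment stopped on 25 March. COVID-19 could therefore have delayed re-randomization mainly in those 17.
- **Few records are exposed.** Someone who leaves during Period 2 is not randomized to Period 3, so the cap restricts the Week 12 label to Study Days 77 to 84. A subject who continues has a scheduled Week 12 visit, which takes precedence. A value at full period length would usually be a scheduled visit with its nominal label.
- **No test depends on it.** SAP 7 makes the Period 2 and 3 endpoints descriptive. A subject who enters Period 2 has normally had a scheduled Week 6 visit, so the Week 6/Week 10 overlap does not disturb the primary analysis. All assessments are listed, so a mislabelled record can be seen.
- **Dilution is not shown.** A reader might infer that short-exposure values dilute the switch to active drug and the withdrawal effect. For Period 2 responder proportions this fails. SAP 5.2.5 uses the number randomized as denominator and values are not imputed, so including an ET value can only raise the count or leave it unchanged. For mean changes the claim would need a time course of ALP onset and offset that the documents do not give.

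What remains is that the rule as written gives wrong labels under delay and has gaps and overlaps that no other rule resolves.

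**Conclusion.** The windowing rule is wrong as written for subjects re-randomized late, and the point is minor. Each day of delay removes one day from the time in period needed for a Week 12 or Week 18 label. The 14-to-21-day figure rests on an assumed delay of the same length. Re-randomization dates already keep most values in the correct period, so the error is mainly in the visit within the period. The exceptions are the Week 6/Week 10 overlap and the subject who does not enter Period 3.

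The effect is confined to descriptive Week 12 and Week 18 summaries and end-of-period proportions. The documents do not establish that any record is affected, or which way a bias would run.

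**What to change.** Define the Period 2 and 3 windows on period day, that is, date minus first dose date of that period, plus 1:

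- Weeks 8 and 14: period days 2 to 20.
- Weeks 10 and 16: period days 21 to 34.
- Weeks 12 and 18: period day 35 onward. End Week 12 at Period 3 randomization or, for a subject not randomized to Period 3, at period day 42 in place of Study Day 84. End Week 18 at exit, as now. Without the limit at day 42, a late off-drug value could enter Week 12.
- State that values up to and including the re-randomization date belong to the earlier period. If dosing starts after that date, let Weeks 8 and 14 open the day after re-randomization, as they do now, so that no day is left out.

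These are the widths Period 1 already uses, and day 42 mirrors its own cap. For on-time subjects first dosed on Study Days 43 and 85 the present edges return: 43 + 21 − 1 = 63, 43 + 35 − 1 = 77, 43 + 42 − 1 = 84, 85 + 21 − 1 = 105, 85 + 35 − 1 = 119. Because the count starts at 1, a visit exactly six weeks after first dose is day 43 in any period, so the SAP should say whether the caps are meant to exclude it.

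The cost is six table rows and the matching derivation code. No new data are needed, since SAP 3.3.7 already uses first and last dosing days within each period for exposure.

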For subjects participating in the PK substudy, additional blood samples for PK analysis will be collected, processed, and sent to the designated central laboratory. PK samples will be collected at the following timepoints (see Table 1PK):

- Pre-dose
- 1, 2, 3, 4, 6, and 8 hours post-dose

Subjects participating in the PK substudy will be required to maintain a dosing diary. The date and time of each dose of study medication taken on the last 3 days prior to the Week 6 visit must be recorded, and the diary must be brought back to the site at the Week 6 clinic visit.

Following the successful completion of all Baseline procedures, the subject will self-administer the first dose of the study medication, consisting of 4 tablets, under the supervision of study personnel. The subject will be provided an entire 6-week supply of study medication consisting of a total of 90 dosage units, each containing 4 tables. The subject will be instructed to swallow the contents of one dosage unit containing 4 tablets in the morning, and one dosage unit containing 4 tablets in the evening, each day until they return to the investigational site 6 weeks later for the next visit. Subjects will be instructed to contact the investigational site immediately if any problems or concerns arise.

5.1.3 Double-Blind Treatment Period - Weeks 2, 4, and 6

During the double-blind treatment period, the following procedures and assessments will be conducted on Weeks 2 and 4:

- Subjects are required to provide blood samples for CBC, CMP, and Lipids. This will not require a visit to the study site and will involve local sample collection.
- Subjects will be contacted by the Investigator, or one of their staff, to discuss the occurrence of any AEs, any new or changes in concomitant medications, adherence to the treatment schedule, and compliance with the requirement to visit a pre-specified clinical laboratory for CBC, CMP, and Lipids. Any new medications that are being taken are, by default, to be considered as being necessitated by an AE. If necessary, subjects may be asked to visit the investigational site, at the Investigator's discretion.

• It is recognized that some investigational sites may require subjects to come to the clinic for these visits and related activities.

During the double-blind treatment period, the following procedures and assessments will be conducted during the visit to the investigational site on Weeks 6:

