6.9 LIVER ADVERSE EVENTS

The following algorithm will be used to monitor for drug-induced liver injury (DILI):

If isolated transaminase (AST or ALT) elevations are observed, defined as: Normal bilirubin and absence of clinical hepatitis, AND

- 1. ALT or AST \geq 5 times the ULN if normal at baseline, OR
- 2. ALT or AST \geq 3 times the baseline or \geq 400 U/L if abnormal at baseline

Then

- 1. Repeat liver profile (ALT, AST, bilirubin and PT/INR) within 2 to 3 days, AND
- 2. Monitor the patient with laboratory testing and physical examination 2 to 3 times per week as per the "close observation" definition in the DILI guidance (https://www.fda.gov/downloads/Drugs/.../Guidances/UCM174090.pdf).

If any ONE of the following criteria is met:

- Transaminases (ALT or AST \geq 3 x baseline) AND bilirubin (total bilruibin \geq 2 x ULN), OR
- Cholestatic markers (ALP or GGT > 2 x baseline), OR
- Isolated ALT/AST ≥ 8x ULN or 600 U/L in the presence of normal CPK and LDH and not secondary to cholangitis, OR
- INR increase > 1.5 refractory to vitamin K administration

OR: if any ONE of the following criteria is met for total bilirubin unrelated to hemolysis:

- 1. Doubling of total bilirubin
 - OR: any increase in total bilirubin if there are symptoms of clinical hepatitis (e.g., vomiting, nausea, right upper quadrant pain),
 - OR: there are immunological reactions (rash or >5% eosinophilia),

Then

- 1. study medication must be interrupted, and
- 2. a drug-induced liver injury workup must be initiated for alternate etiologies;
- 3. repeat a liver profile (ALT, AST, total bilirubin, direct bilirubin, ALP) and PT/INR within 48 to 72 hours;
- 4. monitor the patient with further laboratory testing and physical examination 2 to 3 times per week as per the "close observation" definition in the DILI guidance (https://www.fda.gov/downloads/Drugs/.../Guidances/UCM174090.pdf.
- 5. If a subject lives in a remote area, they can be tested locally and the results communicated to the investigator promptly.

Rechallenge

- 1. Only if a firm alternate etiology is identified AND liver tests have returned to baseline (a rechallenge may be considered)
- 2. If cholangitis is the etiology diagnosis must be firmly established according to the protocol definition before a rechallenge is considered

Rechallenge is not recommended if it is determined that the subject has had a drug induced liver injury.

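### SAP 3.3.6 visit windows fail for subjects who do not enter the next period: ET and unscheduled values on Days 43–62 or 85–104 map to no visit, and the caps sit one day off the study-day formula (minor)

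*SAP*

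**What the plan says.** SAP 3.3.6 keeps the nominal label for scheduled visits and uses windows for the rest: "Unscheduled and early termination (ET) visits will be windowed based on study day, according to the table below". The Week 6 window runs from Day 35 to the date of randomization to Period 2, with a fallback: "If subject is not randomized to Period 2, use study day 42 as upper limit". The Week 12 row has the parallel fallback: "If subject is not randomized to Period 3, use study day 84 as upper limit".

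The next rows are Week 8, given as "date of randomization to Period 2) + 1 – 62", and Week 14, given as "date of randomization to Period 3) + 1 – 104". Neither has a fallback for a subject without the date. The Week 10, 16 and 18 rows start on fixed days (63, 105 and 119) and carry no condition on period.

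SAP 3.3.7 counts the first-dose day as Day 1 and has no Day 0: "Study Day = event date – date of Day 1 (+ 1 if event date" is on or after Day 1. Protocol 5.1.2 has the first dose taken at the Baseline visit, then dosing "each day until they return to the investigational site 6 weeks later for the next visit". The schedules label Baseline differently: Day 0 in SAP 1.2, and Day 0/1 in protocol Table 1.

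**The concern.** ET records are one of the two record types the table exists to place, yet the table is complete only for subjects who continue. For a subject who stops at or near the end of a period, three things go wrong.

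- The window closes before or on the target day, depending on the day convention, and accepts nothing after it.
- The following 20 days belong to no visit.
- After that, the fixed rows resume and label values as visits of a period the subject never entered. SAP 5 has no treatment group for such a subject in that period.

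The trigger is also unclear. SAP 1.1 and 3.2 describe randomization at Week 6 only for subjects who were on placebo; HTD1801 subjects simply continue. The schedules mark Randomization at Week 6 without that limit. On the narrow reading, a continuing HTD1801 subject is not randomized to Period 2, so the Day 42 cap applies to that subject but not to a continuing placebo subject.

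Records of this kind can arise. Protocol 6.9 requires sites, after certain liver findings, to "repeat a liver profile (ALT, AST, total bilirubin, direct bilirubin, ALP) and PT/INR within 48 to 72 hours", which produces off-schedule ALP. Protocol 7.1 keeps some subjects in the study after they stop drug, and SAP 1.1 expects COVID-19 restrictions to disrupt clinic visits. Without a rule, a programmer must decide case by case where a Week 6 or Week 12 value goes.

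**Working it through.** **1. Where 42 and 84 come from.** 7 × 6 = 42 and 7 × 12 = 84. The fixed windows follow the same count: Week 4 is 21–34 (28 − 7 to 28 + 6), Week 10 is 63–76 (70 − 7 to 70 + 6), and Week 16 is 105–118 (112 − 7 to 112 + 6). The caps are therefore a 7 × week count without the + 1.

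**2. On-time visits under SAP 3.3.7.** A visit exactly w weeks after the first dose has Study Day 7w + 1.

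- Week 6: 42 + 1 = 43, one day past the cap of 42.
- Week 12: 84 + 1 = 85, one day past the cap of 84.

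The two conventions differ by one day. Even on the 7 × week count, the fallback Week 6 window (35–42) allows 7 days before target and none after, whereas Week 4 allows 7 before and 6 after.

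**3. The 3.3.6 table applied literally to ET and unscheduled records.** The Period 2 and Period 3 randomization dates are taken as Days 43 and 85 where they exist.

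| Study Day | Never in Period 2 | In Period 2, not Period 3 | In both |
|---|---|---|---|
| 35–42 | Week 6 | Week 6 | Week 6 |
| 43 | none | Week 6 | Week 6 |
| 44–62 | none | Week 8 | Week 8 |
| 63–76 | Week 10 | Week 10 | Week 10 |
| 77–84 | Week 12 | Week 12 | Week 12 |
| 85 | none | none | Week 12 |
| 86–104 | none | none | Week 14 |
| 105–118 | Week 16 | Week 16 | Week 16 |
| 119 on | Week 18 | Week 18 | Week 18 |

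Gap lengths: 62 − 43 + 1 = 20 days and 104 − 85 + 1 = 20 days. A subject in both periods has no gap. Labels from periods never entered: Days 63–84 and 105 onward for a subject never in Period 2; Days 105 onward for a subject in Period 2 but not Period 3.

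**4. Effect of moving the caps alone.** With limits of 43 and 85, Days 44–62 and 86–104 remain unmapped: 62 − 44 + 1 = 19 and 104 − 86 + 1 = 19 days. The later rows therefore need an explicit rule as well.

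**5. Which records are exposed.** Only ET or unscheduled values from a subject with no scheduled value at that visit, because 3.3.6 keeps nominal labels and prefers a scheduled value. A subject who attends the Week 6 visit and then declines Period 2 has a nominal Week 6 value on whatever day it falls.

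**The case against.** The strongest objection concerns consequence. SAP 3.3.7 defines the study visit as the nominal CRF visit, and 3.3.6 speaks of summary displays. The MMRM may therefore use nominal visits only, and the windows may never touch the primary model. This stands. A reader might infer that primary-endpoint data or power would be lost; the documents do not support that. They leave open which rule defines visit in the MMRM, they give no count of affected records, and neither lists ALP among the assessments of a termination visit.

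The cap may also be deliberate. The schedules' Day 0 label and the 7 × week windows fit it, and the SAP states no target Study Day. A reader might infer that 42 is simply wrong; what is supported is a one-day conflict of conventions that must be reconciled.

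Most of each gap arguably should stay out of the summaries, since a value well after the end of a period may be off drug. Agreed: the fix below leaves 19 of the 20 days in each gap as listed only. The gain is one day per window and a stated rule in place of silence.

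Mislabelled later values are largely contained, because Period 2 and 3 tables are grouped by treatments these subjects never received. That is fair, but a label with no column to go in still needs a decision.

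Finally, a reader might infer that the Day 42 cap falls on all HTD1801 subjects and so treats the arms unequally. The wording of SAP 1.1 and 3.2 allows this, but the schedules point the other way, continuing subjects have nominal Week 6 visits, and it is probably not intended.

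**Conclusion.** The table is wrong as written, but the point is minor. For subjects without the next randomization date, ET and unscheduled values on Days 43–62 or 85–104 have no visit, later values take labels from periods never entered, and the caps conflict by one day with the SAP's own study-day formula. This rests on a literal reading of 3.3.6 and, for Days 43 and 85, on first dose at Baseline and return exactly 6 and 12 weeks later.

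Nominal visits are unaffected. The number of records is unknown and probably very small. An effect on the primary MMRM is possible but not shown, and no effect on power is claimed. The reason to act is pre-specification: the placement of a Week 6 or Week 12 value should not be left to a case-by-case decision.

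**What to change.** Before unblinding, edit SAP 3.3.6:

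1. Set the fallback upper limits to Study Day 43 for Week 6 (subject did not enter Period 2) and Study Day 85 for Week 12 (subject entered Period 2 but not Period 3), consistent with 3.3.7.
2. Apply the Week 8–12 windows only to subjects who entered Period 2, and the Week 14–18 windows only to subjects who entered Period 3. State that ET or unscheduled values after the last applicable limit are listed only.
3. Define entry to a period, in all arms, by the first dose date of that period, and use that date in the table in place of the randomization date.
4. State whether windowed ET and unscheduled values enter the MMRM, or whether its visit factor uses nominal visits only.

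The cost is an edit to one table, a sentence on the MMRM, and a small programming change. The downside is that one extra day is accepted as Week 6 or Week 12, and values after the limit stay out of the summaries, now by explicit rule.
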